Respiratory rate, heart rate, systolic and diastolic blood pressure, peripheral capillary oxygen saturation, arterial blood gaseous were obtained before beginning of the ventilation procedure and at 1 hour of ventilation. At these points, HACOR score, dyspnea scale using Visual Analogue Scale (VAS) and Likert scale were also obtained.

Dyspnea score measured using an unmarked 10cm VAS card that had mark with “I can breathe normally”, at one end correspond to patients’ normal baseline breathing which score “0” and on the other end “I can’t breathe at all”, which score “10” represent the worst difficulty perceived by patients [2].

HACOR is an acronym for heart rate, acidosis (pH), consciousness (GCS), oxygenation (PF ratio) and respiratory rate in which each parameter is an independent predictor for NIV failure [9]. HACOR score is out of 25 with differential weighting of each parameter. A HACOR score > 5 at 1 hour of NIV predicts > 80% risk of NIV failure and that early intubation guided by this score significantly improved mortality [3].

Study End Points

The primary outcome was a reduction in respiratory rate from prior to randomization to at 1 hour of treatment. The respiratory rate was measured directly by investigators, who auscultated and counted the breaths sound for

one full minute with a stethoscope. Secondary outcomes were improvements in (1) heart rate; (2) HACOR score; (3) arterial oxygenation PaO₂; (4) PF ratio; (5) dyspnea score; (6) intubation rate and (7) mortality rate 28-days.

Sample Size

Sample size calculation was obtained using G*Power Software version 3.1.9.4 by Franz Faul, University of Kiel, Germany (Copyright 1992-2019). Based on previous work, after 1 hour of intervention, there is a reduction in respiratory rate from 31 breaths/min (SD 3.7) to 22 breaths/min (SD 4.1) in HFNC group compared with a reduction of only 31 breaths/min (SD 3.9) to 25 (SD 3.6) breaths/min in control group [4]. We calculated sample size of 94 patients per group is necessary to get a trial power of 90%, a 1% type I error (2-sided tests) and 10% attrition rate.

Statistical Analysis Plan:

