Data analyses were performed using SPSS (Ver.22 2013 IBM Corporation, USA). Data were analysed on the basis of priori-modified intention to treat. For continuous variables, results for each group are presented as means (SD) or median (interquartile range), according to the data distribution shape and type (nominal or ordinal). Dichotomous data are presented as number and percentage.

Primary outcome of respiratory rate difference and other normally distributed secondary outcomes were calculated using repeated measure ANOVA, a generalized mixed model with a compound-symmetry covariance matrix. Ordinal or skewed numerical data were analysed using Mann-Whitney U Test. Chi-square tests (or two-tailed Fisher exact tests when appropriate) were performed for categorical data. All tests were two-tailed with p-value of less than 0.05 were considered statistically significant.

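### Ordinal or skewed secondary outcomes go to an unadjusted Mann-Whitney test although a baseline is recorded, and for numerical outcomes the choice of test rests on unspecified skewness

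*Combined protocol and SAP*

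**What the plan says.** The Statistical Analysis Plan fixes repeated-measures ANOVA for the primary outcome, respiratory rate. For secondary outcomes it sets up two branches. In one, "other normally distributed secondary outcomes were calculated using repeated measure ANOVA". In the other, "Ordinal or skewed numerical data were analysed using Mann-Whitney U Test". Categorical outcomes go to chi-square or Fisher tests. No secondary outcome is assigned to a branch by name. There is no normality test, skewness threshold, transformation or effect measure, and baseline adjustment is not mentioned.

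The paragraphs just before Study End Points state that vital signs and blood gases "were obtained before beginning of the ventilation procedure and at 1 hour of ventilation". They continue: "At these points, HACOR score, dyspnea scale using Visual Analogue Scale (VAS) and Likert scale were also obtained". Study End Points then lists the secondary outcomes: "Secondary outcomes were improvements in (1) heart rate; (2) HACOR score; (3) arterial oxygenation", followed by PF ratio, dyspnoea score, intubation and 28-day mortality. So five of the seven secondary outcomes are numerical or ordinal with a recorded baseline, and two are binary.

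**The concern.** Three things are left open for those five outcomes.

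- **Baseline.** Mann-Whitney compares two sets of ranks and has no place for a covariate. A baseline that has already been measured therefore cannot be used to reduce residual variation or to correct chance imbalance.
- **Variable.** The text does not say what is ranked. Because the outcomes are defined as improvements, change scores are as natural a reading as 1-hour values.
- **Choice of test.** For a numerical outcome, observed shape decides between a contrast of mean change and a comparison of ranks. These are different targets of estimation, and no rule says when one gives way to the other. Nor does the plan say whether HACOR (scored out of 25) or the dyspnoea VAS counts as ordinal.

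At stake are the precision of the physiological and symptom results and a clear statement of what each result estimates.

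**Working it through.** **Inputs from the documents.** Two-sided alpha of 0.05 (Statistical Analysis Plan); 1:1 allocation (Methods); 94 per group including 10% attrition (Sample Size). Evaluable number per arm: 94 × 0.90 = 84.6, taken as 85.

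**The plan's own figure.** The stated 94 is not reproduced from the 1-hour summary values: HFNC "from 31 breaths/min (SD 3.7) to 22 breaths/min (SD 4.1) in HFNC group", control 25 (SD 3.6) at 1 hour. The difference is 25 − 22 = 3, the pooled SD is √((4.1² + 3.6²)/2) = 3.86, and d = 0.78. At 90% power and 1% two-sided alpha this gives 51 per group by the t calculation, or 57 after 10% attrition. The mismatch concerns the primary outcome and does not bear on this point; 94 is used here only as the planned size.

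**Assumptions not in the documents.** A treatment effect of 0.45 SD on the 1-hour value, a pre-post correlation ρ of 0.3, 0.5 or 0.6, and equal SDs at the two times.

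**Formula.** Power ≈ Φ(λ − 1.96), with λ = 0.45 × √(85 × e / (2v)). Here v is the variance relative to the 1-hour value: 1 for the 1-hour value, 2(1 − ρ) for change, and 1 − ρ² after baseline adjustment. The factor e is 0.955 for Mann-Whitney under normality and 1 otherwise.

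Example for ρ = 0.5. Mann-Whitney on the 1-hour value: λ = 0.45 × √(85 × 0.955 / 2) = 2.87, power 0.82. ANCOVA: λ = 0.45 × √(85 / 1.5) = 3.39, power 0.92.

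The formula was checked by simulation (3,000 trials per setting, bivariate normal):

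| Analysis | ρ = 0.3: formula / simulated | ρ = 0.5: formula / simulated | ρ = 0.6: formula / simulated |
|---|---|---|---|
| Mann-Whitney, 1-hour value | 0.82 / 0.82 | 0.82 / 0.81 | 0.82 / 0.81 |
| Mann-Whitney, change | 0.68 / 0.67 | 0.82 / 0.82 | 0.89 / 0.89 |
| t-test on change (group-by-time test of repeated-measures ANOVA) | 0.70 / 0.69 | 0.83 / 0.83 | 0.91 / 0.90 |
| ANCOVA on baseline | 0.87 / 0.86 | 0.92 / 0.92 | 0.96 / 0.95 |

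**In sample-size terms.** Mann-Whitney on 1-hour values needs 1 / (0.955(1 − ρ²)) times the patients of ANCOVA: 1.15 at ρ = 0.3, 1.40 at 0.5, 1.64 at 0.6. On changes the factor is 2 / (0.955(1 + ρ)): 1.61, 1.40 and 1.31.

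**Skewed data.** Normal data are not the case for which the plan reserves Mann-Whitney, so the comparison was repeated on lognormal data (84 per arm, 0.4 SD shift, 4,000 trials, ρ = 0.3 / 0.5 / 0.7). Power was 0.70 / 0.72 / 0.72 for Mann-Whitney on 1-hour values, 0.58 / 0.72 / 0.90 on changes, and 0.77 / 0.85 / 0.96 for ANCOVA on the log scale. The ordering is the same.

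**Type I error.** A mechanical rule (Shapiro-Wilk at 5% in each arm, then the change t-test or 1-hour Mann-Whitney) rejected a true null in 4.6-5.8% of trials. Reporting whichever of those two tests had the smaller p-value rejected in about 9-10%. If the pair is the change t-test and Mann-Whitney on change, the figure is about 5.5-6.5%.

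**The case against.** Mann-Whitney is a conventional and valid test for ordinal or skewed data in a randomised trial, and the gain from covariate adjustment is one of efficiency. That stands: the point is an improvement in method and specification, not a correction of an invalid test.

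Four stronger readings are tempting, and the documents do not support them.

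- **That ordinal outcomes are switched after the data are seen.** The plan sends ordinal data to Mann-Whitney by variable type. Only numerical secondary outcomes depend on observed shape.
- **That the baseline is discarded.** This is true only if 1-hour values are ranked. Ranked changes use the baseline by subtraction but do not adjust for it.
- **That moving from ANOVA to Mann-Whitney causes the power loss.** With two time points, the group-by-time test of repeated-measures ANOVA is the t-test on change. Against that, Mann-Whitney on 1-hour values gains power at ρ = 0.3 (0.82 against 0.69), is about level at 0.5, and loses about 9 points at 0.6. The loss in the table comes from not adjusting for baseline, which the ANOVA branch does not do either.
- **That false positives rise to 9-10%.** This requires deliberate selection of the smaller p-value, and nothing in the plan says that. Judging shape and then choosing leaves the error near 5%.

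**Conclusion.** The point holds as a limited one. Five secondary outcomes have a recorded baseline and no named test; those analysed by Mann-Whitney would be unadjusted under either reading of what is ranked. At 85 per arm, baseline adjustment raises power from about 81% (1-hour values) or 67-89% (changes) to 86-95%. For numerical outcomes the estimand is also left to an unspecified judgement of skewness.

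The percentages rest on the assumed 0.45 SD effect and ρ of 0.3-0.6. Over that range ANCOVA has more power than either Mann-Whitney analysis, but the margin varies: it is smallest against 1-hour values when ρ is low and against changes when ρ is high. No material inflation of type I error is shown. The primary outcome, intubation and mortality are not touched. The change is worth making because it is cheap, not because the trial's main conclusion is at risk.

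**What to change.** In the Statistical Analysis Plan, name for each secondary outcome the variable, the effect measure and one baseline-adjusted model, before outcomes are compared by arm:

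- Heart rate and dyspnoea VAS: ANCOVA of the 1-hour value on its baseline, reported as an adjusted mean difference.
- PaO2 and PF ratio: the same on the log scale, reported as an adjusted ratio.
- HACOR: proportional-odds regression with baseline HACOR as covariate, reported as an odds ratio.

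Remove the choice of test by skewness. Keep Mann-Whitney as a sensitivity analysis, stating whether it ranks 1-hour values or changes.

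The cost is SAP wording and standard SPSS procedures; no further data or patients are needed. The downsides are a proportional-odds assumption for HACOR, which should be checked, and results for PaO2 and PF ratio expressed as ratios instead of differences.

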Official Title of the study:

Helmet CPAP versus High Flow Nasal Cannula Oxygen in Acute
Cardiogenic Pulmonary Oedema: A Randomized Control Trial

Date of Document:

31st May 2018

Objective:

To our knowledge, there has been no randomized trial comparing hCPAP with HFNC for management of patients with ACPE. The aim of this study was to compare the effectiveness of hCPAP with HFNC in emergency department in the management of ACPE, in terms of physiological outcomes, patient's comfort, intubation rate, and 28-days mortality.

Design:

This is a single center, randomized, controlled trial. The study was conducted from January 2018 to December 2018 in Emergency Department, Raja Permaisuri Bainun Hospital, Perak, Malaysia

Methods:

A randomization sequence was generated using Microsoft Excel Version 14.3.9 (Microsoft Corporation Redmond, WA) using permuted block randomization technique. Sequentially numbered, sealed and opaque envelopes were used to conceal randomized allocation. The person responsible for the randomization was not part of the clinical team. Participants were assigned to receive either helmet CPAP or HFNC in a 1:1 ratio.

Ethical approval from Medical Research and Ethics Committee of Malaysia Ministry of Health had been granted [NMRR-17-1839-36966 (IIR)]. Written informed consent was obtained from patient whenever possible or from the next of kin. An external data monitoring committee supervised data collection.

Participants

All patients diagnosed with ACPE was defined by sudden onset of dyspnea; presence of bilateral rales on auscultation, compatible physical examination (elevated jugular venous pressure, third heart sound on cardiac auscultation) with no medical history suggesting pulmonary aspiration or infection; or congestion found on chest radiograph [1].

Patients meeting all the following inclusion criteria (1) age \geq 18 years (2) respiratory rate $>$ 30 breath per minute and (3) pulse oximetry saturation (SpO_2)

< 90% with oxygen > 5 L per minute via reservoir facemask were included. Patient were excluded if they have one or more of the following criteria (1) altered mental status (GCS \leq 14) (2) need for urgent intubation (3) hemodynamically unstable, or (4) pulmonary edema was believed to be non-cardiogenic causal.

Protocol

Upon arrival patients were supported on high flow non-rebreathing facemask with reservoir of oxygen 15 L/min. After enrolment they were randomized to receive either hCPAP or HFNC.

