The helmet (CASTAR, Starmed, Italy) has gas inlet and outlet ports. The inlet port was connected to air and oxygen blender (Air Liquide, France). The outlet port was connected to a mechanical spring PEEP valve. Patient neck circumference was measured to ensure a tight but comfortable seal. The gas flow was set at minimum 40 L/min. PEEP was initially set at 5 cmH₂O with increments of 3-5 cmH₂O to achieve oxygen saturation of 94 -97%. Inspired oxygen fraction (FiO₂) was set at 0.6 and maintained throughout the treatment.

HFNC (Hamilton, C3S, INTELLiVENT, Switzerland) consists of an air-oxygen blender, which permits accurate adjustment of FiO₂ between 0.21 and 1.0 and delivery of gas flow up to 60 L/min through a heated humidifier (Hamilton H900, Switzerland). The gas mixture flows through a circuit at temperature of 37 °C and an absolute humidity of 44 mg/L to the patients. Large or medium nasal cannula were chosen according to patients' nostril size to limit air contamination. HFNC was first set at a gas flow of 50 L/min and a FiO₂ of 1.0, then was titrated to maintain SpO₂ of 94 – 97%.

In addition to the study intervention, patients received standard treatment consists of intravenous infusion of isosorbide dinitrate at initial rate of 1mg/hr, increased up to 10 mg/hr. Intravenous furosemide bolus of 40 mg or equal to patient pre-existing oral dosage were given if systolic blood pressure > 100 mmHg [1]. No sedative agent was given to patients. After the end of 60-

minute protocol, the chosen modality was continued at the discretion of the treating physician.

Early termination criteria included failure to tolerate NIV, worsening of respiratory failure (respiratory > 35 breaths/min, SpO₂ < 92%, PF ratio < 200, or signs of increased work of breathing such as use of accessory muscle), pulse rate > 120 beat/min or 30% increased above baseline, mean arterial pressure (MAP) increased > 30% above baseline prior intervention and deterioration of conscious level. If one or more of the criteria were encountered, intervention was escalated to intubation and mechanical ventilation. These patients were excluded from the final data analyses. The decision was made by the managing physician without the involvement of the researcher team.

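### Intubation and 28-day mortality are compared without the baseline severity already recorded: a valid test, but one prespecified covariate could add modest precision

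*Combined protocol and SAP*

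**What the plan says.** Study End Points lists seven secondary outcomes. The last two, "6) intubation rate and (7) mortality rate 28-days", are the only binary ones, and both also appear in the Objective. The Statistical Analysis Plan does not name them, but as dichotomous outcomes they fall under its sentence "Chi-square tests (or two-tailed Fisher exact tests when appropriate) were performed for categorical data". It summarises dichotomous data as counts and percentages. It plans no risk difference, no confidence interval and no adjusted model for them.

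Baseline severity is collected. In the Protocol section, vital signs and arterial blood gases "were obtained before beginning of the ventilation procedure and at 1 hour of ventilation", and the text continues: "At these points, HACOR score, dyspnea scale using Visual Analogue Scale (VAS) and Likert scale were also obtained". Of HACOR it says that "each parameter is an independent predictor for NIV failure".

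Methods describes permuted-block allocation in a 1:1 ratio with sealed envelopes, and mentions no stratification. On patients who meet an early termination criterion and are escalated to intubation, the Protocol section says: "These patients were excluded from the final data analyses".

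**The concern.** The plan identifies a severity measure that it regards as prognostic, measures it before treatment in every patient, and then leaves it out of the two comparisons that matter most to patients. Neither outcome was used to size the trial, so both comparisons will be imprecise. Adjusting for a prognostic pre-treatment variable usually narrows the interval around a risk difference and needs no new data. What is at stake is some precision on two secondary outcomes. The validity of the planned test is not in question.

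**Working it through.** **Plan's own figure.** There is none to reproduce for these outcomes: no event rate, effect size or power is given for intubation or mortality. The 94 per group in Sample Size was derived for respiratory rate and includes 10% attrition. It enters here only as the number analysed: 94 × 0.9 = 84.6, taken as 85 per arm.

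**Power of the crude test** (two-sided 0.05, 85 per arm, assumed rates):

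| Assumed rates | Expected events | Power |
|---|---|---|
| 10% v 5% | 85 × 0.15 ≈ 13 | 0.23 |
| 20% v 10% | 85 × 0.30 ≈ 26 | 0.45 |
| 30% v 15% | 85 × 0.45 ≈ 38 | 0.65 |

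**Effect of adjustment.** Each setting was simulated 1,500 times with one standard-normal baseline covariate. Logit slopes of 0.5, 1.0 and 1.5 per SD were used, that is odds ratios of e^0.5 = 1.65, e^1.0 = 2.7 and e^1.5 = 4.5. The crude risk difference was compared with the standardised risk difference from a logistic model with arm and covariate. Relative efficiency is RE = Var(crude)/Var(adjusted), and the variance cut is 1 − 1/RE.

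| Assumed rates | RE, slope 0.5 (cut) | RE, slope 1.0 (cut) | RE, slope 1.5 (cut) |
|---|---|---|---|
| 5% v 5% | 0.989 (−1.1%) | 1.026 (2.5%) | 1.161 (13.9%) |
| 10% v 3% | 1.000 (0%) | 1.062 (5.8%) | 1.128 (11.3%) |
| 10% v 5% | 1.019 (1.9%) | 1.063 (5.9%) | 1.172 (14.7%) |
| 20% v 10% | 1.026 (2.5%) | 1.109 (9.8%) | 1.299 (23.0%) |
| 30% v 15% | 1.041 (3.9%) | 1.187 (15.8%) | 1.304 (23.3%) |

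A second simulation at 85 per arm gave cuts of about 0–3% for slopes 0.3–0.5, 5–13% for slope 1.0 and 10–25% for slope 1.5. The two sets agree to within a few percentage points, which is the simulation error to expect with 1,500 runs.

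**Interval width.** Width scales with the square root of the variance. A 3% cut narrows the interval by 1 − √0.97 = 1.5%. Cuts of 5% and 13% narrow it by 2.5% and 6.7%, and a 25% cut by 1 − √0.75 = 13.4%.

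**Power, crude to adjusted.**
- 10% v 5%: 0.21 to 0.24 (slope 0.5 or 1.0); 0.23 to 0.28 (slope 1.5).
- 20% v 10%: 0.46 to 0.47, 0.44 to 0.50 and 0.46 to 0.54 for the three slopes.
- 30% v 15%: 0.66 to 0.68, 0.72 and 0.79.

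**Model failure.** Across the covariate strengths tried, including none, the adjusted fit failed or separated in 104–116 of 1,500 runs (6.9–7.7%) at 10% v 3%. The figures were 38–49 (2.5–3.3%) at 5% v 5% and 12–26 (0.8–1.7%) at 10% v 5%. No fit failed at 20% v 10% or 30% v 15%.

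**How strong is the covariate likely to be?** The documents do not say. The only quantified statement, "A HACOR score > 5 at 1 hour of NIV predicts > 80% risk of NIV failure", is about the score after randomisation. Participants excludes anyone with a GCS of 14 or below, so the consciousness component is the same for everyone at baseline. It also requires a respiratory rate above 30, which truncates another component. The predictor statement concerns NIV failure, so it bears on intubation more directly than on death at 28 days.

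**The case against.** The strongest reply is that nothing is wrong. Allocation is concealed and 1:1, so the crude test has its stated type I error, and its interval already allows for chance imbalance. These are secondary outcomes on which the trial was not sized, and adjusting them is a preference. That stands, and it limits the point to an optional improvement.

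Four stronger readings are tempting, and the documents support none of them.

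- A reader might infer that unstratified randomisation lets imbalance in severity bias these comparisons. It does not: imbalance between randomised groups adds variance, which adjustment can reduce, but it does not shift the expected result.
- A reader might take intubation and death to be the rarest outcomes, and so the ones where adjustment helps most. No event rates are given, and the table shows the gain to be smallest at rates of 10% or less.
- A reader might carry the 80% figure for HACOR over to the baseline score. It belongs to the 1-hour score, which treatment can alter and which must not be a covariate.
- A reader might expect adjustment to rescue these outcomes. Taken literally, the early termination rule removes intubation events from the intubation comparison and makes mortality conditional on a post-randomisation event. That is the larger problem. A narrower interval around such a comparison could reassure falsely.

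One part of the reply fails. At slope 1.0 or above, none of the settings in the table showed a loss of precision. At slope 0.5 the worst result was a 1.1% increase in variance. The expected cost in precision is therefore negligible.

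**Conclusion.** The point holds as a low-priority improvement. The planned chi-square or Fisher test is valid but leaves unused a baseline measure that the plan itself calls prognostic. The likely gain is modest: about 0–3% lower variance for a weak covariate, about 5–13% for a moderate one, and up to about 25% only for a strong covariate with event rates near 20%. These figures assume 85 analysed per arm, a single normally distributed covariate, and event rates and slopes that the documents do not supply. Support is better for intubation than for mortality. None of it applies until it is settled which patients are in the analysis.

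**What to change.** First reconcile the exclusion in the Protocol section with intubation as an endpoint and with the modified intention-to-treat analysis in the Statistical Analysis Plan.

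Then add to the Statistical Analysis Plan, before outcomes are seen by arm:

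- For intubation and for 28-day mortality, fit a logistic model with arm and one fixed covariate, pre-treatment HACOR. The 1-hour score is never used.
- Report the standardised risk difference with 95% CI, naming the interval method, alongside the chi-square or Fisher result.
- If the model separates or does not converge, report the crude risk difference with the Fisher test.
- State which result is the main one, so that a disagreement is not settled after the fact.

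The cost is a few sentences, no new data, and a standardisation step beyond a routine logistic fit. The downside is occasional non-convergence when events are very few. The document is dated 31 May 2018 and the study ran from January to December 2018, so a change made after that date falls after the study's start. The timing relative to any look at outcomes by arm should be recorded.

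### The sample size is set at a two-sided 1% type I error, but the analysis plan tests everything, the primary outcome included, at two-sided 5%

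*Combined protocol and SAP*

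**What the plan says.** - **Study End Points** names one primary outcome: "The primary outcome was a reduction in respiratory rate from prior to randomization to at 1 hour of treatment".
- **Sample Size** plans on that outcome only, with 94 patients per group, 90% power and "a 1% type I error (2-sided tests) and 10% attrition rate". The planning figures are a "reduction in respiratory rate from 31 breaths/min (SD 3.7) to 22 breaths/min (SD 4.1) in HFNC group" against "31 breaths/min (SD 3.9) to 25 (SD 3.6) breaths/min in control group".
- **Statistical Analysis Plan** assigns the primary outcome a method but no significance level of its own: "Primary outcome of respiratory rate difference and other normally distributed secondary outcomes were calculated using repeated measure ANOVA". The section ends with a single rule: "All tests were two-tailed with p-value of less than 0.05 were considered statistically significant".

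Nothing elsewhere in the document mentions an interim analysis, a division of alpha, an adjustment for the seven secondary outcomes, or a reason for planning at a level stricter than the one used for testing.

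**The concern.** The level at which the primary test is judged decides whether the trial is reported as positive. Here the design section gives a false-positive risk of 1% and the analysis section gives 5%. Sidedness does not explain the gap: both levels are two-sided, and a one-sided against two-sided mix-up would produce a factor of 2, not 5.

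Two things follow. A primary p-value between 0.01 and 0.05 can be read either way, and whoever reads it will already have seen the result. Also, the stated 90% power belongs to a 1% test, so it does not describe the test that the analysis section specifies.

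**Working it through.** **1. Does the stated sample size show which alpha was meant?**

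The planning difference is (31 − 22) − (31 − 25) = 9 − 6 = 3 breaths/min. The normal-approximation formula per group is n = 2(z₁₋α/₂ + z₀.₉₀)² SD²/3², then divided by 0.90 for attrition. The multiplier 2(z₁₋α/₂ + z₀.₉₀)² is 2(2.576 + 1.282)² = 29.76 at 1% and 2(1.960 + 1.282)² = 21.01 at 5%.

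- Pooled 1-hour SD: √[(4.1² + 3.6²)/2] = 3.86. At 1%, n = 29.76 × 14.885/9 = 49.2, so 50, and 50/0.90 gives 56. At 5%, n = 34.8, so 35, and 35/0.90 gives 39. Neither is 94.
- SD of change: √[mean over arms of (s₀² + s₁² − 2·r·s₀·s₁)], where r is the correlation between the baseline and 1-hour values, which the documents do not give. r = 0 gives 5.42, r = 0.13 gives 5.05 and r = 0.5 gives 3.84. With 5.05 at 1%, n = 29.76 × 25.50/9 = 84.3, so 85, and 85/0.90 = 94.4.
- A generic standardised effect of 0.5 at 5%: n = 21.01/0.25 = 84.1, so 85, and 85/0.90 = 94.4.

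The figure of 94 can thus be reached about equally well at 1% and at 5%, each time with an input that the plan does not state. It cannot settle which alpha was intended.

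**2. Where the two rules disagree**

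The evaluable number is 94 × 0.90 = 84.6, taken as 85 per arm (168 degrees of freedom). The comparison is treated as a two-sample t-test on the change. With complete data at two time points, this is the group-by-time test of the planned model.

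The smallest significant difference is t × SD × √(2/85):

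- α = 0.05: 1.974 × 0.1534 = 0.303 SD
- α = 0.01: 2.605 × 0.1534 = 0.400 SD

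An observed difference between about 0.30 and 0.40 SD of the change is therefore positive by one section and negative at the level of the other, whatever the SD is.

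**3. How often a result falls there**

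If there is no true difference, the chance is 5% − 1% = 4%. For a real difference, the chance is noncentral-t power at 5% minus power at 1%. The SD of change is an assumption, so a range is shown.

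| Assumed SD of change | Disputed zone, breaths/min | True difference 3: power 5% / 1% | In zone | True difference 2: power 5% / 1% | In zone |
|---|---|---|---|---|---|
| 3.86 (r about 0.5) | 1.17–1.54 | 99.9% / 99.3% | 0.6% | 91.9% / 77.9% | 14% |
| 5.05 (r about 0.13) | 1.53–2.02 | 97.1% / 89.6% | 7.5% | 72.8% / 49.2% | 24% |
| 5.42 (r = 0) | 1.64–2.17 | 94.8% / 84.1% | about 11% | 66.7% / 42.3% | 24% |

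The 3 breaths/min columns follow the plan's own figures. The 2 breaths/min columns show a smaller true effect and are illustrative.

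**4. A check that needs no SD**

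With 85 per arm, the standardised effect that gives 90% power at 1% is 0.598. Its power at 5% is 97.2%. So if 90% is correct for a 1% test, the test in the analysis plan has about 97%.

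**The case against.** The strongest reply is that the document contains only one decision rule, the one in the Statistical Analysis Plan. The 1% is an input to a sample-size program, and nothing says that the primary result will be declared at that level. An analyst following the document would test at 5%. The mismatch is also in the safe direction: a trial sized at 1% and tested at 5% has more power than stated, and 5% is a conventional level. All of this stands. It limits the consequence but does not remove the conflict, because no text gives the analysis section precedence or says that 1% was chosen only to be conservative.

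Three further points are fair:

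- The larger probabilities rest on assumptions. At 3 breaths/min and SD 3.86 the chance of a disputed result is only 0.6%. The SD of 5.05 was picked because it reproduces 94 at 1%, so it presupposes that 1% was used. If 94 came instead from a 5% calculation, the 97% figure does not apply and the 1% may be a slip.
- 85 per arm may be optimistic. The Protocol section removes patients who meet early termination criteria from the final analyses, and nothing shows that these fit within the 10% attrition.
- Much of the document is in the past tense, so the analysis may already have been done. However, it is dated 31 May 2018, within the stated January to December 2018 conduct period, so the past tense does not show that a correction came too late.

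**Conclusion.** The concern holds. The two sections give different type I error rates for the same primary test, 1% and 5%, and nothing in the document reconciles them. This needs no assumption, and neither does the 4% chance of a disputed result under no true difference. The 0.30 to 0.40 SD zone assumes 85 evaluable patients per arm. The figures in breaths/min and the probabilities under a real effect also depend on the assumed SD and true difference, so the practical effect could be small or substantial. The 5% test is valid and the trial is not underpowered by the mismatch. It should be fixed because the criterion for success on the primary outcome should be stated once, before the result is known.

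**What to change.** Before the data are analysed, state the same alpha for the primary outcome in both sections. The document does not show which was intended, so the sponsor should choose without sight of results by arm.

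- **Option (a), keep 1%.** Replace the last sentence of the Statistical Analysis Plan with: *The primary outcome is tested at a two-sided level of 0.01, as in the sample-size calculation; every other test uses a two-sided level of 0.05.* The cost is power at 85 per arm. For 3 breaths/min it is 99.3% instead of 99.9% (SD 3.86), 90% instead of 97% (SD 5.05) or 84% instead of 95% (SD 5.42). For 2 breaths/min it is 78% instead of 92%, 49% instead of 73% or 42% instead of 67%.
- **Option (b), keep 5%.** Change the type I error in the Sample Size section to 5% two-sided and restate the power of 94 per group at that level: about 97%, provided that 94 does give 90% at 1%. The cost is giving up the stricter false-positive limit that the design now states. If 1% was only a cautious planning value, it is enough to say so in that section and give the power at 5%.

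Either option takes about one sentence. If the analysis has already been carried out, the report should give the exact primary p-value, state that the plan named both levels, and say how the result reads at each.
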